2.3.3 Clinical Pharmacokinetics

The PK of nivolumab was studied in subjects over a dose range of 0.1 to 10 mg/kg administered as a single dose or as multiple doses of nivolumab every 2 or 3 weeks. The geometric mean (% CV%) clearance (CL) was 9.5 mL/h (49.7%), V_{ss} was 8.0 L (30.4%), and geometric mean elimination half-life ($t_{1/2}$) was 26.7 days (101%). Steady-state concentrations of nivolumab were reached by 12 weeks when administered at 3 mg/kg every 2 weeks, and systemic accumulation was approximately 3-fold. The exposure to nivolumab increased dose proportionally over the dose range of 0.1 to 10 mg/kg administered every 2 weeks. Additionally, nivolumab has a low potential for drug-drug interactions. The clearance of nivolumab increased with increasing body weight. The PPK analysis suggested that the following factors had no clinically important effect on the CL of nivolumab: age (29 to 87 years), gender, race, baseline LDH, PD-L1. A PPK analysis suggested no difference in CL of nivolumab based on age, gender, race, solid tumor type, baseline tumor size, and hepatic impairment.

Although ECOG status, baseline glomerular filtration rate (GFR), albumin, body weight, and mild hepatic impairment had an effect on nivolumab CL, the effect was not clinically meaningful. PPK analysis suggest that nivolumab CL in subjects with cHL was approximately 32% lower relative to subjects with NSCLC; however, the lower CL in cHL subjects was not considered to be clinically relevant as nivolumab exposure was not a significant predictor for safety risks for these patients. When nivolumab is administered in combination with ipilimumab, the CL of nivolumab was increased by 24%, whereas there was no effect on the clearance of ipilimumab. Additionally, PPK and exposure response analyses have been performed to support use of 240 mg every 2 week (Q2W) dosing in addition to the 3 mg/kg Q2W regimen. A flat dose of nivolumab 240 mg Q2W was selected since it is identical to a dose of 3 mg/kg for subjects weighing 80 kg, the observed median body weight in nivolumab-treated cancer patients. Using a PPK model, the overall distributions of nivolumab exposures (C_{avgss} , C_{minss} , C_{maxss} , and C_{min1}) are comparable after treatment with either 3 mg/kg or 240 mg nivolumab. The predicted range of nivolumab exposures (median and 90% prediction intervals) resulting from a 240 mg flat dose across the 35 to 160 kg weight range is maintained well below the corresponding exposures observed with the well tolerated 10 mg/kg nivolumab Q2W dosage.

2.3.4 Pharmacodynamics

The clinical PDs were assessed for nivolumab monotherapy and for nivolumab in combination with ipilimumab.

The PD effects of nivolumab were studied by assessing receptor occupancy (RO), peripheral immune cell population modulation, systemic cytokine modulation, and change in absolute

lymphocyte count (ALC) in two studies. Results were as follows:

- Peripheral RO of PD-1 is saturated at doses ≥ 0.3 mg/kg dose levels as measured on CD3+ cells from frozen and fresh peripheral blood mononuclear cells (PBMCs).
- Nivolumab treatment had no clinically meaningful changes in activated T-cells in peripheral blood; no dose response was evident.
- Baseline measurements of select immune cell subsets were not associated with response to nivolumab.
- Mean ALC measured over time did not change at any nivolumab dose nor was it associated with response to nivolumab.
- Median percent increase from baseline to post-dose for CXCL9 and CXCL10 were consistent with demonstration of immunomodulatory activity of nivolumab on these chemokines.

To understand if the effect of nivolumab in combination with ipilimumab was distinct from that of either nivolumab or ipilimumab monotherapy, changes in immunomodulatory PD biomarkers with combination nivolumab and ipilimumab treatment was assessed in one study. ALC, activated CD4+ and CD8+ T cells in the periphery, and levels of inflammatory cytokines were measured in blood and serum. Results were as follows:

- No consistent rise in ALC was observed with combination nivolumab and ipilimumab therapy, similar to nivolumab monotherapy.
- Increases in activated CD4+ and CD8+ T cells were observed with the combination regimen, consistent with the pharmacodynamic effects of ipilimumab alone and distinct from the effects of nivolumab alone.
- Combination therapy resulted in increases in interferon- γ induced serum cytokines, such as MIG (CXCL9) and IP-10 (CXCL10), which are also increased with single agent nivolumab.

2.3.5 Clinical Efficacy

Nivolumab has demonstrated durable responses exceeding 6 months as monotherapy and in combination with ipilimumab in several tumor types, including NSCLC, melanoma, RCC, cHL, SCLC, gastric cancer, urothelial cancer, HCC, and CRC. In confirmatory trials, nivolumab as monotherapy demonstrated a statistically significant improvement in OS as compared with the current standard of care in subjects with advanced or metastatic NSCLC, unresectable or metastatic melanoma, advanced RCC, or SCCHN. Nivolumab in combination with ipilimumab improved PFS and ORR over ipilimumab alone in subjects with unresectable or metastatic melanoma.

2.3.6 Clinical Safety

The overall safety experience with nivolumab, as a monotherapy or in combination with other therapeutics, is based on experience in approximately 12,300 treated subjects.

For monotherapy, the safety profile is similar across tumor types. There is no pattern in the incidence, severity, or causality of AEs to nivolumab dose level. In Phase 3 controlled studies, the safety profile of nivolumab monotherapy is acceptable in the context of the observed clinical

efficacy, and manageable using established safety guidelines. Clinically relevant AEs typical of stimulation of the immune system were infrequent and manageable by delaying or stopping nivolumab treatment and timely immunosuppressive therapy or other supportive care.

In several ongoing clinical trials, the safety of nivolumab in combination with other therapeutics such as ipilimumab, cytotoxic chemotherapy, anti-angiogenics, and targeted therapies is being explored. Most studies are ongoing and, as such, the safety profile of nivolumab combinations continues to evolve. The most advanced combination under development is nivolumab with ipilimumab, which is approved in subjects with unresectable or metastatic melanoma, and being studied in multiple tumor types. Results to date suggest that the safety profile of nivolumab with ipilimumab combination therapy is consistent with the mechanisms of action of nivolumab and ipilimumab. The nature of the AEs is similar to that observed with either agent used as monotherapy; however, both frequency and severity of most AEs are increased with the combination.

2.3.7 Flat Dosing

The safety and efficacy of 240 mg Q2W flat dose of nivolumab is expected to be similar to 3 mg/kg Q2W dosing regimen. A flat dose of nivolumab 240 mg Q2W was selected since it is identical to a dose of 3 mg/kg for subjects weighing 80 kg, the observed median body weight in nivolumab treated cancer patients. Using a PPK model, the overall distributions of nivolumab exposures (C_{avgss} , C_{minss} , C_{maxss} , and C_{min1}) are comparable after treatment with either 3 mg/kg or 240 mg nivolumab. The predicted range of nivolumab exposures (median and 90% prediction intervals) resulting from a 240 mg flat dose across the 35 to 160 kg weight range is maintained well below the corresponding exposures observed with the well tolerated 10 mg/kg nivolumab Q2W dosage. Across the various tumor types in the clinical program, nivolumab has been shown to be safe and well tolerated up to a dose level of 10 mg/kg, and the relationship between nivolumab exposure produced by 3 mg/kg and efficacy and safety has been found to be relatively flat. Given the similarity of nivolumab PK across tumor types and the similar exposures predicted following administration of 240 mg flat dose compared to 3 mg/kg Q2W regimen, it is expected that the safety and efficacy profile of 240 mg Q2W nivolumab will be similar to that of 3 mg/kg nivolumab. Hence, a flat dose of 240 mg nivolumab is under investigation.

In addition, nivolumab 480 mg administered once every 4 weeks (Q4W) is currently under investigation. The less frequent dosing regimen is designed to afford more convenience to the target patient populations. The nivolumab dose of 480 mg Q4W was selected based on clinical data and modeling and simulation approaches using PPK and exposure-response analyses of data from studies in multiple tumor types (melanoma, NSCLC, and RCC) to provide an approximately equivalent dose of nivolumab 3 mg/kg Q2W. Exposures following nivolumab 480 mg Q4W regimen are predicted to be within the exposure ranges observed at doses up to 10 mg/kg Q2W used in the nivolumab clinical program, and are not considered to put participants at increased risk.

2.4 Ipilimumab with Nivolumab

2.4.1 Clinical Pharmacokinetics

The pharmacokinetics of nivolumab and ipilimumab were assessed using a PPK approach when nivolumab and ipilimumab were administered in combination. The %CV CL, V_{ss} , and $t_{1/2}$ of nivolumab were 10.0 mL/h (50.3%), 7.92 L (30.1%), and 24.8 days (94.3%), respectively. When ipilimumab 3 mg/kg (registration dose) was administered in combination with nivolumab, the CL of nivolumab was increased by 24%, whereas there was no effect on the CL of ipilimumab. However, co-administration with ipilimumab 1 mg/kg did not appear to have an effect on nivolumab CL. This is unlikely to be clinically relevant given the observed efficacy with the nivolumab and ipilimumab combination regimen.

When administered in combination, the CL of nivolumab increased by 42% in the presence of anti-nivolumab antibodies. There was no effect of anti-ipilimumab antibodies on the CL of ipilimumab.

2.4.2 Immunogenicity

Of 394 patients who were treated with nivolumab in combination with ipilimumab and evaluable for the presence of anti-nivolumab antibodies, 149 patients (37.8%) tested positive for treatment-emergent anti-nivolumab antibodies by an ECL assay and 18 patients (4.6%) had neutralizing antibodies against nivolumab. Of the 391 patients evaluable for the presence of anti-ipilimumab antibodies, 33 patients (8.4%) tested positive for treatment-emergent anti-ipilimumab antibodies by an ECL assay and 1 patient (0.3%) had neutralizing antibodies against ipilimumab. There was no evidence of increased incidence of infusion reactions/hypersensitivity reactions with antinivolumab antibody development. There was no evidence of altered toxicity profile associated with anti-product antibody development and there was no apparent causal effect of neutralizing antibodies on loss of efficacy.

2.4.3 Clinical Efficacy

In trial CA209012 (NCT01454102; CheckMate 012), an ongoing multi-arm phase 1 safety study of nivolumab in chemotherapy-naive NSCLC subjects, 56 subjects were administered nivolumab in combination with chemotherapy (gemcitabine / cisplatin, pemetrexed / cisplatin, carboplatin / paclitaxel), 21 with nivolumab in combination with erlotinib, and 197 with nivolumab in combination with ipilimumab.

A summary of ORR and PFS rate at 12 months for subjects treated with nivolumab plus ipilimumab is provided in the table below. The original nivolumab plus ipilimumab combinations using the same dosing regimens as in the melanoma studies ($n = 49$) were found to be non-tolerable for the NSCLC population, and these regimens were not pursued further. The results from newer combination dosing regimens (arms N, O, P, Q; $n = 148$) with lower and less frequent dosing of ipilimumab are presented below. The cohorts containing the approved dose of nivolumab (3 mg/kg) demonstrated improved ORR and PFS compared to the cohorts containing the lower dose of nivolumab (1 mg/kg).

The regimens for these cohorts were:

- Arm N ($n=31$): nivolumab 1 mg/kg + ipilimumab 1 mg/kg every 3 weeks for 4 cycles, followed nivolumab 3 mg/kg every 2 weeks

- Arm O (n=40): nivolumab 1 mg/kg every 2 weeks + ipilimumab 1 mg/kg every 6 weeks
- Arm P (n= 38): nivolumab 3 mg/kg every 2 weeks + ipilimumab 1 mg/kg every 12 weeks
- Arm Q (n=39): nivolumab 3 mg/kg every 2 weeks + ipilimumab 1 mg/kg every 6 weeks

Table 2: Efficacy in Chemotherapy-Naive NSCLC Subjects Treated with Nivolumab and Ipilimumab								
Treatment Group	N	Nivolumab (mg/kg)	ORR^a		PFS at 12 months		Median OS	
			n (%)	95% CI^b	%	95% CI^c	Months	95% CI^b
Nivo 1 + Ipi 1 ×4 (arm N)	31	1	6 (19)	8, 38	30	14, 47	NR	11.5, NR
Nivo 1 + Ipi 1 (arm O)	40	1	13 (33)	19, 49	25	12, 42	NR	11.0, NR
Nivo 3 + Ipi 1 q12w (arm P)	38	3	18 (47)	31, 64	48	31, 63	NR	14.1, NR
Nivo 3 + Ipi 1 q6w (arm Q)	39	3	15 (39)	23, 55	35	20, 50	18.1	13.3, 18.1

Database Lock Date 18-Feb-2016

a. CR + PR; assessed according to RECIST v.1.1
 b. Based on Kaplan-Meier method
 c. Based on Greenwoods formula

Abbreviations: CI = confidence interval; Ipi = ipilimumab; Nivo = nivolumab; NR: not reached; ORR = objective response rate; PFSR = progression-free survival rate; OS = overall survival

2.4.4 Clinical Safety

The original nivolumab plus ipilimumab combinations using the same dosing regimens as in the melanoma studies were found to be non-tolerable for the NSCLC population, so 4 additional regimens were examined (arms N, O, P, Q), and the results from these newer cohorts are presented. The regimens for these cohorts were:

- Arm N (n=31): nivolumab 1 mg/kg + ipilimumab 1 mg/kg every 3 weeks for 4 cycles, followed nivolumab 3 mg/kg every 2 weeks
- Arm O (n=40): nivolumab 1 mg/kg every 2 weeks + ipilimumab 1 mg/kg every 6 weeks
- Arm P (n= 38): nivolumab 3 mg/kg every 2 weeks + ipilimumab 1 mg/kg every 12 weeks
- Arm Q (n=39): nivolumab 3 mg/kg every 2 weeks + ipilimumab 1 mg/kg every 6

The most frequently reported drug-related adverse events (AEs) in the newer nivolumab plus ipilimumab cohorts were fatigue (29.0%), diarrhea (25.0%), pruritus (23.7%), and fatigue (23.1%) in arms N, O, P, Q, respectively. Drug-related serious adverse events (SAEs) reported in more than 2 subjects/cohort treated in the newer nivolumab plus ipilimumab cohorts were adrenal insufficiency, hypophysitis, pneumonitis, autoimmune hepatitis, diarrhea, colitis, and acute kidney injury.

Drug-related AEs leading to discontinuation reported in more than 1 subject treated in the new

nivolumab plus ipilimumab arms included ALT increased, AST increased, colitis, myalgia, pneumonitis, rash, autoimmune hepatitis, infusion-related reaction, facial nerve disorder, esophagitis, and transaminases increased.

Most deaths were due to disease progression. The only deaths reported due to study drug toxicity were in the nivolumab + ipilimumab original treatment groups (respiratory failure following Grade 3 colitis, pulmonary hemorrhage, and toxic epidermal necrolysis in a patient with history of ulcerative colitis).

2.5 Correlative Studies Background

Baseline and on-treatment tumor biopsies will be evaluated for all participants, as well as an optional time of progression tumor biopsy. Biopsies are planned pre-treatment, approximately 4 weeks post initiation of therapy, and at the time of disease progression. To perform immunoprofiling, tissue will be subjected to:

- **Flow cytometry.** This will assess for immune cell lineages (e.g. T cells, B cells, neutrophils, macrophages, dendritic cells, NK cells, etc.) as well as characterization of CD4+ and CD8+ T cells, including their differentiation status (e.g. FOXP3, CCR7, CD45RA, CD45RO), expression of activation markers (e.g. CD69, CD11a, CD38) and inhibitory receptors (e.g. PD-1, TIM-3, LAG-3, CTLA-4), and their proliferation (e.g. Ki-67).

If adequate tissue and resources are available, samples may also undergo:

- **Microfluidic culture.** Primary tumor spheroids in microfluidic culture will be exposed to CTLA-4 or PD-1 inhibitors and we will then observe whether engulfment of spheroids by macrophage-like cells occurs over time. We will also perform cytokine profiling of conditioned media from these samples.
- **Ex vivo cytokine analysis.** The cytokine release studies will study 15-20 different cytokines and their relationship with patient outcomes, with the overarching hypothesis that change in cytokines over time will be associated with outcome to therapy with immune checkpoint inhibition.

Additional biomarkers may be analyzed as deemed appropriate at the time of analysis. Furthermore, tumor and germline whole exome sequencing (WES) as well as single cell RNA sequencing will be performed. To perform WES, nucleic acid (DNA and RNA) will be obtained from tumor cellular material using standard operating procedures. For clinical tumor specimens, a “high-coverage” sequencing approach will be utilized, which should yield an average coverage of 150-200 fold; paired normal DNA will be sequenced to a depth of approximately 80-100-fold. WES data will be analyzed for base mutations, small insertions/deletions, and copy number alterations. RNA sequencing will be done to examine gene expression changes and pathway adaptation on-treatment as compared to pre-treatment.

Results from flow cytometry and cytokine analyses (if performed) will be compared to clinical outcomes. For the flow cytometric immunoprofiling on tumor and immune cells, t-distributed neighbor embedding (t-SNE) analyses will be performed, resulting in the identification of “hot”

and “cold” clusters^{5,6}. Each of the immunologic markers/parameters will be analyzed individually and in compilation to form such clusters. We hypothesize that outcomes may vary according to the value of such markers and/or hot/cold cluster status.

Peripheral blood mononuclear cells (PBMCs) as well as plasma will be collected from whole blood to assess immune cell populations and cytokines and other biomarkers of interest as appropriate. Surface staining with a panel of antibodies and intracytoplasmatic cytokine staining followed by flow cytometry will be performed on the PBMC samples. Different T cell populations, their activation status, and the production of different cytokines as well as other immune cell populations including myeloid-derived suppressor cells (MDSCs) will be characterized. MDSCs are a heterogeneous group of immature cells which are greatly expanded in experimental models of cancer. Studies in humans have reported increased frequencies as well as immune-suppressive properties in some of the myeloid-derived subsets of MDSCs present in the peripheral blood of patients with various forms of cancer^{14,15}. To further explore the relationship of immune cell populations and their potential correlation to clinical outcomes, peripheral blood levels will be serially collected from patients enrolled to the trial.

3. PARTICIPANT SELECTION

3.1 Eligibility Criteria

3.1.1 Histologically confirmed stage IV NSCLC, with no prior systemic anti-cancer therapy of any kind (including *EGFR* and *ALK* inhibitors). Prior definitive chemoradiation for locally advanced disease is permitted as long as the last administration of chemotherapy or radiation (whichever was given last) occurred at least 6 months prior to enrollment. Prior adjuvant or neoadjuvant chemotherapy for early stage lung cancer is permitted if completed at least 6 months prior to initiating study treatment.

3.1.2 Participants must have measurable disease, defined as at least one lesion that can be accurately measured in at least one dimension (longest diameter to be recorded for non-nodal lesions and short axis for nodal lesions) as ≥ 20 mm with conventional techniques or as ≥ 10 mm with spiral CT scan, MRI, or calipers by clinical exam. See **Section 11** for the evaluation of measurable disease.

Note: presence of measurable disease must be in at least one lesions that has not been previously irradiated.

3.1.3 Age ≥ 18 years.

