New lesions are considered measurable at the time of initial progression if the longest diameter is at least 10 mm (except for pathological lymph nodes which must have a short axis of at least 15 mm). Any new lesion considered non-measurable at the time of initial progression may become measurable and therefore included in the tumor burden if the longest diameter increases to at least 10 mm (except for pathological lymph nodes which must have a short axis of at least 15 mm). In situations where the relative increase in total tumor burden by 10% is solely due to inclusion of new lesions which become measurable, these new lesions must demonstrate an absolute increase of at least 5 mm.

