11.1.1 Definitions

Evaluable for Target Disease response. Only those participants who have measurable disease present at baseline, have received at least one cycle of therapy, and have had their disease re-evaluated will be considered evaluable for target disease response. These participants will have their response classified according to the definitions stated below. (Note: Participants who exhibit objective disease progression prior to the end of cycle 1 will also be considered evaluable.)

Evaluable Non-Target Disease Response. Participants who have lesions present at baseline that are evaluable but do not meet the definitions of measurable disease, have received at least one cycle of therapy, and have had their disease re-evaluated will be considered evaluable for non-target disease. The response assessment is based on the presence, absence, or unequivocal progression of the lesions.

Unevaluable patients will be included in the analysis of response as non-responders assuming they were eligible and received study drug.

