11.1.2 Disease Parameters

Measurable disease. Measurable lesions are defined as those that can be accurately measured in at least one dimension (longest diameter to be recorded) as ≥ 20 mm by chest x-ray or ≥ 10 mm with CT scan, MRI, or calipers by clinical exam. All tumor measurements must be recorded in millimeters (or decimal fractions of centimeters).

Note: Tumor lesions that are situated in a previously irradiated area are not considered measurable unless there has been demonstrated growth in the lesion.

Malignant lymph nodes. To be considered pathologically enlarged and measurable, a lymph node must be ≥ 15 mm in short axis when assessed by CT scan (CT scan slice

thickness recommended to be no greater than 5 mm). At baseline and in follow-up, only the short axis will be measured and followed.

Non-measurable disease. All other lesions (or sites of disease), including small lesions (longest diameter <10 mm or pathological lymph nodes with ≥ 10 to < 15 mm short axis), are considered non-measurable disease. Bone lesions, leptomeningeal disease, ascites, pleural/pericardial effusions, lymphangitis cutis/pulmonitis, inflammatory breast disease, abdominal masses (not followed by CT or MRI), and cystic lesions are all considered non-measurable.

Note: Cystic lesions that meet the criteria for radiographically defined simple cysts should not be considered as malignant lesions (neither measurable nor non-measurable) since they are, by definition, simple cysts.

‘Cystic lesions’ thought to represent cystic metastases can be considered as measurable lesions, if they meet the definition of measurability described above. However, if non-cystic lesions are present in the same participant, these are preferred for selection as target lesions.

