11.1.3.1 Evaluation of Target Lesions

Complete Response (CR): Disappearance of all target lesions. Any pathological lymph nodes (whether target or non-target) must have reduction in short axis to <10 mm.

Partial Response (PR): At least a 30% decrease in the sum of the diameters of target lesions, taking as reference the baseline sum diameters.

Progressive Disease (PD): At least a 20% increase in the sum of the diameters of target lesions, taking as reference the smallest sum on study (this includes the baseline sum if that is the smallest on study). In addition to the relative increase of 20%, the sum must also demonstrate an absolute increase of at least 5 mm. (Note:

the appearance of one or more new lesions is also considered progressions).

Stable Disease (SD): Neither sufficient shrinkage to qualify for PR nor sufficient increase to qualify for PD, taking as reference the smallest sum diameters while on study.

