11.1.3.2 Evaluation of Non-Target Lesions

Complete Response (CR): Disappearance of all non-target lesions and normalization of tumor marker level. All lymph nodes must be non-pathological in size (<10 mm short axis).

Note: If tumor markers are initially above the upper normal limit, they must normalize for a patient to be considered in complete clinical response.

Non-CR/Non-PD: Persistence of one or more non-target lesion(s) and/or maintenance of tumor marker level above the normal limits.

Progressive Disease (PD): Appearance of one or more new lesions and/or *unequivocal progression* of existing non-target lesions. *Unequivocal progression* should not normally trump target lesion status. It must be representative of overall disease status change, not a single lesion increase.

Although a clear progression of “non-target” lesions only is exceptional, the opinion of the treating physician should prevail in such circumstances, and the progression status should be confirmed at a later time by the review panel (or Principal Investigator).

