11.1.3.4 Evaluation of Best Overall Response

The best overall response is the best response recorded from the start of the treatment until disease progression/recurrence (taking as reference for progressive disease the smallest measurements recorded since the treatment started). The patient's best response assignment will depend on the achievement of both measurement and confirmation criteria.

Table 17: For Participants with Measurable Disease (i.e., Target Disease)

Target Lesions	Non-Target Lesions	New Lesions	Overall Response	Best Overall Response when Confirmation is Required*
CR	CR	No	CR	≥ 4 wks Confirmation**
CR	Non-CR/Non-PD	No	PR	≥ 4 wks Confirmation**
CR	Not evaluated	No	PR	
PR	Non-CR/Non-PD/not evaluated	No	PR	Documented at least once ≥ 4 wks from baseline**
SD	Non-CR/Non-PD/not evaluated	No	SD	
PD	Any	Yes or No	PD	no prior SD, PR or CR
Any	PD***	Yes or No	PD	
Any	Any	Yes	PD	

* See RECIST 1.1 manuscript for further details on what is evidence of a new lesion.

** Only for non-randomized trials with response as primary endpoint.

*** In exceptional circumstances, unequivocal progression in non-target lesions may be accepted as disease progression.

Note: Participants with a global deterioration of health status requiring discontinuation of treatment without objective evidence of disease progression at that time should be reported as “*symptomatic deterioration*.” Every effort should be made to document the objective progression even after discontinuation of treatment.

Table 18: For Participants with Non-Measurable Disease (i.e., Non-Target Disease)

Non-Target Lesions	New Lesions	Overall Response
CR	No	CR
Non-CR/non-PD	No	Non-CR/non-PD*
Not all evaluated	No	not evaluated
Unequivocal PD	Yes or No	PD
Any	Yes	PD

* ‘Non-CR/non-PD’ is preferred over ‘stable disease’ for non-target disease since SD is increasingly used as an endpoint for assessment of efficacy in some trials so to assign this category when no lesions can be measured is not advised

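### Section 3.1.2 admits a 10 mm short-axis node on CT as measurable disease, but 11.1.2 requires 15 mm, so a patient with no target lesion can be enrolled in a response-rate trial

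*Combined protocol and SAP*

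**What the plan says.** **Entry.** Section 3.1.2 requires at least one measurable lesion, taking the longest diameter for non-nodal lesions and the short axis for nodes. It then gives one pair of size limits for both: "short axis for nodal lesions) as ≥ 20 mm with conventional techniques or as ≥ 10 mm with spiral CT scan", with MRI and calipers sharing the 10 mm limit. It refers the reader to Section 11 for evaluating measurable disease and does not say which section prevails if they differ.

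**Response assessment.** Section 11.1.2 treats nodes separately: "a lymph node must be ≥ 15 mm in short axis when assessed by CT scan". It places smaller enlarged nodes in the other class: "pathological lymph nodes with ≥ 10 to < 15 mm short axis), are considered non-measurable disease". Section 5.5.1 uses the same nodal limit for new lesions after progression: "except for pathological lymph nodes which must have a short axis of at least 15 mm".

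**Scoring without measurable disease.** Section 11.1.1 has a category for "Participants who have lesions present at baseline that are evaluable but do not meet the definitions of measurable disease", provided they have had at least one cycle and been re-evaluated. Section 11.1.3.4 gives their response table, "Table 18: For Participants with Non-Measurable Disease (i.e., Non-Target Disease"), in which complete response is the only outcome that counts as a response. Sections 11.1.1 and 13.1.2 count unevaluable patients as non-responders; 11.1.1 adds the condition that they were eligible and received study drug.

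**Primary analysis.** Sections 13.1.2 and 13.1.3 analyse eligible and treated patients. Stage 2 opens at 15 or more responses in 43, and the combination is judged worthy of further study at 29 or more in 80.

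**The concern.** An investigator who completes the eligibility checklist from 3.1.2 can properly enrol a stage IV patient whose only candidate lesion is a node of 10 to under 15 mm on CT. Under Section 11 that patient has no measurable disease and so no target lesion. Partial response is defined as "At least a 30% decrease in the sum of the diameters of target lesions", so it is not available to that patient.

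Two things follow. The trial can enrol a patient who lacks the ordinary route to its primary endpoint. And the patient's membership of the primary set is open: eligible if 3.1.2 governs, ineligible and outside the set if 11.1.2 governs. The result is read against fixed counts in an open-label, single-arm trial, so that choice should not be left until responses are known.

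**Working it through.** **1. The thresholds side by side (node on CT, short axis)**

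| Short axis | 3.1.2 | 11.1.2 |
|---|---|---|
| under 10 mm | not measurable | not measurable |
| 10 to under 15 mm | measurable | non-measurable |
| 15 mm or more | measurable | measurable |

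The sections disagree only in the middle row.

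**2. How such a patient could respond.** With no target lesion, the remaining route is a non-target complete response, confirmed by a second scan (13.1.2). For nodes, 11.1.3.2 requires: "All lymph nodes must be non-pathological in size (<10 mm short axis"). The fall needed to get below 10 mm is more than (14 − 10)/14 = 28.6% from 14 mm and more than (14.9 − 10)/14.9 = 32.9% from 14.9 mm. Over most of the range this is less than the 30% that a partial response needs, but not over all of it. All other non-target disease must also disappear, which should be uncommon in stage IV disease.

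**3. Reproduce the design.** Inputs from 13.1.2: null rate 0.30, target rate 0.44, stage 1 of 43 (continue at 15 or more), total 80 (success at 29 or more). With X1 ~ Bin(43, p) and X2 ~ Bin(37, p):

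P(success) = Σ (x = 15 to 43) P(X1 = x) · P(X2 ≥ 29 − x)

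| Quantity | Stated | Exact |
|---|---|---|
| Type I error (p = 0.30) | 0.109 | 0.1092 |
| Power (p = 0.44) | 88% | 0.8838 |
| Early stop under the null, P(X1 ≤ 14) | 0.71 | 0.7081 |

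All three agree.

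**4. One affected patient.** Let this patient respond with probability c, and all others at 0.44 (power) or 0.30 (type I error). If the patient is in stage 1, X1 becomes Bin(42, p) + Bernoulli(c); if in stage 2, X2 becomes Bin(36, p) + Bernoulli(c). The boundaries do not change. The values of c are assumptions.

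| c | Power, stage 1 / stage 2 | Type I error, stage 1 / stage 2 |
|---|---|---|
| 0 | 0.859 / 0.876 | 0.093 / 0.099 |
| 0.10 | 0.865 / 0.878 | 0.099 / 0.102 |
| 0.20 | 0.870 / 0.880 | 0.104 / 0.106 |

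The largest loss of power is 0.8838 − 0.8594 = 0.0244, or 2.4 points.

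**5. An assumed share of such patients.** If a share f enters this way and all are non-responders, the overall rate is p(1 − f).

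- f = 1/80 = 1.25%: the rate is 0.44 × 0.9875 = 0.4345, power 0.866, type I error 0.096.
- f = 2/80 = 2.5%: the rate is 0.44 × 0.975 = 0.429, power 0.846, type I error 0.085.

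**The case against.** The strongest reply is that the documents already deal with this patient. The pointer in 3.1.2 leads to a section with its own nodal definition, 5.5.1 uses the same 15 mm, and the wording of 3.1.2 looks merely loose. That makes Section 11 the more natural authority, but nothing states that it prevails, and 3.1.2 reads as complete in itself.

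A reader might go further and infer that the plan does not say how such a patient is scored. The documents do not support that. If 3.1.2 governs, then 11.1.1, Table 18 and 13.1.2 together score the patient: non-target evaluable after at least one cycle and re-evaluation, and otherwise a non-responder. If 11.1.2 governs, the patient is ineligible and outside the primary set. The gap is narrower: which threshold decides eligibility.

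A reader might also infer a material inflation of type I error, because a complete response by a small node can need less shrinkage than a partial response. If one such patient were certain to be scored as a complete response, type I error would be 0.147 (stage 1) or 0.134 (stage 2). That certainty is not credible when all other non-target disease must disappear too. One such patient raises type I error above 0.109 only if the chance of a confirmed complete response exceeds the null rate of 30%.

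What stands of the reply is that the effect is small and probably conservative. It does not remove the contradiction.

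**Conclusion.** The contradiction between 3.1.2 and 11.1.2 is real. Followed as written, 3.1.2 can admit a patient who has no target lesion and whose place in the primary set is unsettled. This is a minor consistency correction.

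One such patient costs at most 2.4 points of power. With a response chance of 0 to 20%, type I error stays between 0.093 and 0.106, below the design value. These figures assume one affected patient, all others at the design rates, and unchanged boundaries. The documents give no count of such patients; stage IV disease with no other measurable lesion is probably rare. The losses would be smaller if the 44% target already allows for such patients.

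It would be wrong to conclude that the design is miscalculated: the stated power, type I error and early-stopping probability all reproduce.

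**What to change.** In 3.1.2, keep 10 mm or more for non-nodal lesions and use the 11.1.2 threshold for nodes: 15 mm or more in short axis by CT.

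Add one sentence to 13.1.2: anyone already enrolled on a node of 10 to under 15 mm alone stays in the primary denominator and is scored by the existing rules in 11.1.1, Table 18 and 13.1.2. Do not write a new definition of unevaluable. A rule based only on whether the patient was re-imaged, for example, would conflict with the one-cycle condition in 11.1.1 and with the row of Table 18 for incompletely evaluated lesions.

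The cost is a short amendment and at most a few more screen failures. Sample size and both boundaries stay as they are.
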